## 4.3.11.3 Handling of Dropouts and Missing Data

See Section 4.3.11.2.

## 4.3.11.4 Primary Analysis of Secondary Endpoint

The analysis of PFS is based on the Full analysis set. The number and percentage of subjects experiencing a PFS event (broken down by type of event/censoring) are provided along with the median PFS and its two-sided 95% CI estimated using the Kaplan-Meier method. Kaplan-Meier plots of PFS are presented. Moreover, the landmark estimates of PFS at 3, 6, 9, and 12 months from first dose are summarised.

The treatment status at progression of subjects at the time of analysis are summarised. This includes the number (%) of subjects who were on treatment at the time of progression, the number (%) of subjects who discontinued study treatment prior to progression, the number (%) of subjects who have not progressed and were on treatment or discontinued treatment.

A summary of 'potential' duration of follow-up for PFS is included using median (range). This is presented for censored subjects (including all types of PFS censoring).

# 4.3.12 Secondary Endpoint: Overall Survival

OS is a secondary efficacy endpoint.

## 4.3.12.1 Definition

OS is defined as the time from the date of first dose of Cycle 0 until death due to any cause regardless of whether the subject withdraws from study therapy or receives another anti-cancer therapy.

## 4.3.12.2 Derivations

OS (months) = (date of death or censoring – date of first dose+ 1) / (365.25/12)

Any subject not known to have died at the time of analysis is censored based on the last recorded date on which the subject was known to be alive.

Note: Survival calls are made in the week following the date of DCO for the analysis, and if subjects are confirmed to be alive or if the death date is post the DCO date these subjects are censored at the date of DCO. The status of ongoing, withdrawn (from the study) and "lost to follow-up" subjects at the time of any formal OS analysis should be obtained by the

site personnel by checking the subject's notes, hospital records, contacting the subject's general practitioner and checking publicly-available death registries. In the event that the subject has actively withdrawn consent to the processing of their personal data, the vital status of the subject can be obtained by site personnel from publicly available resources where it is possible to do so under applicable local laws.

Note: For any other OS analysis performed, in the absence of survival calls being made, it may be necessary to use all relevant CRF fields to determine the last recorded date on which the subject was known to be alive for those subjects still on treatment (since the *SURVIVE* module is only completed for subjects off treatment if a survival sweep is not performed). The last date for each individual subject is defined as the latest among the following dates recorded on the CRFs:

- AE start, stop and change in severity dates
- Admission and discharge dates of hospitalisation
- Study treatment date
- End of treatment date
- Concomitant medication start and stop dates
- Laboratory test dates
- Date of vital signs
- Date of ECGs
- Physical examination dates
- Cardiovascular data
- Disease assessment dates on RECIST CRF
- Start and stop dates of alternative anticancer treatment
- Date last known alive on survival status CRF
- End of study date (excluding patients lost to follow-up)
- Patient Reported Outcomes (PRO) questionnaire dates

The proportion of subjects alive at 6, 9, 12, and 18 months is defined as the Kaplan-Meier estimate of OS at that particular month.

"Potential" duration of follow-up for OS, applicable only for OS censored subjects, is defined as follows:

Potential duration of follow-up for OS (months) = (date of OS censoring [date last known to be alive] – date of first dose + 1) / (365.25/12).

## 4.3.12.3 Handling of Dropouts and Missing Data

If a subject is known to have died where only a partial death date is available, then the date of death will be imputed as the latest of the last date known to be alive +1 from the database and the death date using the available information provided:

- a. For Missing day only using the  $1^{st}$  of the month.
- b. For Missing day and Month using the 1st of January.

If death has been recorded but the date is entirely missing, then date of death will be imputed as the date the patient was last known to be alive +1.

## 4.3.12.4 Primary Analysis of Secondary Endpoint

The analysis of OS is based on the Full analysis set. The number and percentage of subjects experiencing an OS event and Kaplan-Meier plots of OS are presented. Additionally, summaries of the numbers and percentages of subjects who have died, those still in survival follow-up, those lost to follow-up and those who have withdrawn consent are provided. The median OS and two-sided *95*% CI are estimated using the Kaplan-Meier method.

Moreover, the landmark estimates of OS at 6, 9, 12, and 18 months from first dose are summarised with corresponding 95% CI.

A summary of the potential duration of follow-up for OS is included using median (range). This is presented for censored subjects.

#### 4.3.12.5 Sensitivity Analyses of the Secondary Endpoint

A sensitivity analysis is conducted to assess the potential impact of COVID-19 related deaths on OS. That is, subjects who had a death event where the primary or secondary cause was COVID-19 infection or COVID-19 infection was reported as a fatal AE, are censored at the date of their COVID-19 infection related death. If less than five events appear and less than 2% of enrolled subjects are affected the sensitivity analysis will not be carried out.

## 4.3.12.6 Supplementary Analyses of the Secondary Endpoint

Not applicable

## 4.3.13 Secondary Endpoint: PK of ceralasertib

PK of ceralasertib alone and when in combination with durvalumab is a secondary endpoint.

See section 4.5

## 4.3.14 Safety Analysis

The domain safety covers exposure, adverse events, clinical laboratory, vital signs, and electrocardiogram (ECG).

Tables are provided for the safety set, listings are provided for all subjects or the safety set depending on the availability of data.

#### 4.3.14.1 Exposure

#### 4.3.14.1.1 Definitions and Derivations

For the below derivations exposure will be calculated from Cycle 1 onwards i.e. Cycle 0 will not be counted.

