# 3.2.2 Study Treatment

During Cycle 0, patients will be treated with ceralasertib 240 mg BD, as oral tablets, from Days 1 to 7, Q28D, followed by an off-treatment period between Days 8 to 28 (i.e. no-dose period). From Cycle 1, patients will be treated with the combination of ceralasertib 240 mg BD, oral tablets, from Days 1 to 7, plus durvalumab 1500 mg Day 8, as an IV infusion, Q28D, until progressive disease (confirmed RECIST 1.1-defined radiological progression), unacceptable toxicity, withdrawal of consent, or if a study treatment discontinuation criterion is met.

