# 3.2.4 On-treatment

For the purposes of summarizing safety data assessed at visits, in addition to baseline data, only on-treatment data are included in the summary tables. On-treatment data is defined as data on/after the first dose of study treatment (including Cycle 0) and with assessment date up to and including the date of last study treatment + 90 days (safety follow-up), and prior to the start of any subsequent anti-cancer therapy.

For biomarker data the on-treatment assessment is strictly defined as Cycle 0 Day 7. The Cycle 0 Days 15 – Day 28 period will be defined as off-treatment.

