# 4.3.1.1 Primary Analysis of Primary Endpoint

All study patients in the biopsy sub-study are required to provide 3 mandatory fresh tumour biopsy samples for testing at Screening (Days -21 to -1) [baseline assessment], onceralasertib treatment, Cycle 0 (on Day 7) of ceralasertib monotherapy [on-treatment assessment], and off-ceralasertib treatment, Cycle 0 (between Days 15 to 28) [off-treatment assessment]. All analysis of this data will be performed on the PD Analysis Set. CD8+ T cells tumour infiltration are summarised descriptively in baseline, ceralasertib ontreatment and ceralasertib off-treatment samples for each of the tests described in Section 4.3.1

The summary statistics provided include number of observations (n), geometric mean (calculated as  $exp[\mu]$ , where  $\mu$  is the mean of the data on a logarithmic scale), coefficient of variation (CV, calculated as 100  $\sqrt{exp(s_2)-1}$ , where s is the standard deviation of the data on a log scale), arithmetic mean, arithmetic SD, median, minimum and maximum.

Boxplots of change from baseline will be produced on a log scale for on-treatment and offtreatment timepoints. The geometric means are presented using a diamond symbol in these plots. These will be produced for each of the tests described in Section 4.3.1.

Plots will be produced showing each patient's baseline, on-treatment and off-treatment results over time on a log scale with separate lines indicating the results for each patient. These will be produced for each of the tests described in Section 4.3.1.

Data are transformed as appropriate e.g., log2-transformation, and analysed by MMRM with fixed effect for timepoint. An unstructured variance-covariance matrix is used to accommodate repeated measures within a subject, assuming model convergence otherwise alternative structures including autoregressive (TYPE=AR(1)), compound symmetry (TYPE=CS), and Toeplitz (TYPE=TOEP) are applied and selected based on best fit by examining best fit statistics AICC.

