## 4.3.11.1 Definition

PFS is defined as the time from first dose of Cycle 0 until the date of first documented disease progression as assessed by investigator or death (by any cause in the absence of disease progression), regardless of whether the subject withdraws from study therapy or receives another anti-cancer therapy prior to progression.

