#### **Duration of exposure**

- Duration of exposure to ceralasertib = min(date of last dose where dose > 0 mg +o21, date of death, date of DCO) - first dose\* date +o1
- Duration of exposure to durvalumab = min(date of last dose where dose > 0 mg  $+\circ 20$ , date of death, date of DCO) first dose\* date  $+\circ 1$

\*First dose refers to earliest dose of either treatment

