## 4.3.14.2 Adverse Events

## 4.3.14.2.1 Definitions and Derivations

The Medical Dictionary for Regulatory Activities (MedDRA) (version 25 or higher) is used to code the AEs. AEs are graded according to the National Cancer Institute Common Terminology Criteria for AEs (CTCAE) (version 5.0).

Treatment emergent adverse events (TEAEs) are all AEs which onset or worsen in severity following the first administration of IP in Cycle 0 within the duration of the treatment period, up to and including 30 days after the last dose of study treatment for ceralasertib monotherapy or 90 days after last dose of study treatment for ceralasertib and durvalumab combination. Worsening in severity is determined by comparison with the pre-treatment CTCAE grade of the AE recorded closest to the start of dosing.

AEs with a missing start time or where time is not collected, which occur on the same day as first IP administration, are reported as treatment emergent.

For rules on missing or partial dates, see Section 3.4.6.

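### Sub-study ceralasertib exposure is derived from Cycle 1 onwards, although the safety data it should describe run from the first Cycle 0 dose

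*SAP*

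**What the plan says.** All references are to the biopsy sub-study SAP.

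- **Treatment (3.2.2).** "During Cycle 0, patients will be treated with ceralasertib 240 mg BD, as oral tablets, from Days 1 to 7, Q28D". Days 8 to 28 of Cycle 0 are dose-free. Durvalumab is added only from Cycle 1, on Day 8.
- **Exposure (4.3.14.1.1).** "For the below derivations exposure will be calculated from Cycle 1 onwards i.e. Cycle 0 will not be counted". The sentence stands above duration, actual exposure, delays, interruptions, cumulative dose and RDI, so it governs all of them.
- **Formulas under that sentence.** Both duration formulas, for ceralasertib and for durvalumab, carry the footnote "First dose refers to earliest dose of either treatment". The intended ceralasertib dose is counted from that drug's own first-dose date, and the actual cumulative dose adds up everything administered. None of the three repeats the Cycle 1 start.
- **Adverse events (4.3.14.2.1).** Treatment-emergent events are those that begin or worsen "following the first administration of IP in Cycle 0 within the duration of the treatment period".
- **Other Cycle 0 origins.** On-treatment safety data (3.2.4) explicitly include Cycle 0. The Safety analysis set (Table 6), which is also the exposure set, needs only one dose. PFS (4.3.11.1) and OS (4.3.12.1) start at the first Cycle 0 dose: "PFS is defined as the time from first dose of Cycle 0".
- **Primary endpoint (4.3.1.1).** The two post-baseline CD8 biopsies are taken on Cycle 0 Day 7 and between Cycle 0 Days 15 and 28.

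The SAP gives no reason for leaving Cycle 0 out and plans no separate Cycle 0 exposure summary.

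**The concern.** An exposure table tells the reader how much drug lay behind the safety findings. Here the findings are collected over one period and the exposure is summarised over a shorter one.

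- A toxicity in Cycle 0 appears in the adverse event tables, but the dosing that preceded it does not enter the derived exposure.
- A ceralasertib interruption in Cycle 0 is not derived. Neither is a late start of Cycle 1, because a delay is measured from Day 1 of the preceding cycle and that cycle is not counted.
- Cycle 0 ceralasertib is the only study drug given before the post-baseline CD8 biopsies, yet no derived summary describes how much of it was taken.

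The silent start dates in the formulas add a second problem: two programmers could implement the section differently.

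**Working it through.** The SAP states no exposure figure, so there is nothing to reproduce. The check applies its own formulas to a fully compliant, on-schedule subject who completes Cycle 0 and then *k* combination cycles. The values of *k* are assumptions.

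**Inputs.** 240 mg twice daily on Days 1 to 7 of a 28-day cycle (3.2.2); duration = last dose date + 21 − first dose date + 1, ignoring death and data cut-off (4.3.14.1.1).

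**One Cycle 0 course.** Dose: 240 × 2 × 7 = 3,360 mg over 7 dosing days. Duration: 7 + 21 − 1 + 1 = 28 days.

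**With *k* combination cycles.** Numbering days from Cycle 0 Day 1, the last ceralasertib dose is on day 28*k* + 7. From Cycle 0 the duration is (28*k* + 7) + 21 − 1 + 1 = 28(*k* + 1). From Cycle 1, which starts on day 29, it is 28*k*. The share omitted is 1/(*k* + 1).

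| *k* | Days from Cycle 0 | Days from Cycle 1 | Duration omitted | mg from Cycle 0 | mg from Cycle 1 |
|---|---|---|---|---|---|
| 0 | 28 | none derivable | all | 3,360 | 0 |
| 1 | 56 | 28 | 50.0% | 6,720 | 3,360 |
| 2 | 84 | 56 | 33.3% | 10,080 | 6,720 |
| 3 | 112 | 84 | 25.0% | 13,440 | 10,080 |
| 6 | 196 | 168 | 14.3% | 23,520 | 20,160 |
| 12 | 364 | 336 | 7.7% | 43,680 | 40,320 |

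**RDI = 100 × delivered / intended.**

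- Cycle 0 dropped from both terms, *k* = 1: 3,360 / 3,360 = 100%.
- Cycle 0 kept in both terms, *k* = 1: 6,720 / 6,720 = 100%.
- Blindness to Cycle 0: a subject takes 4 of 7 Cycle 0 days and one full combination cycle. Over the whole period RDI is (480 × 4 + 3,360) / 6,720 = 5,280 / 6,720 = 78.6%. With Cycle 0 dropped it is 100%.
- Mismatched origins: delivered dose from Cycle 1 over intended dose from Cycle 0 gives 6,720 / 10,080 = 66.7% at *k* = 2. The reverse mismatch gives 6,720 / 3,360 = 200% at *k* = 1 and 13,440 / 10,080 = 133.3% at *k* = 3.

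**What deleting the sentence alone would do to durvalumab.** Its duration would start at Cycle 0 Day 1, because the footnote takes the earlier of the two drugs; that adds 28 days for a subject who goes on to Cycle 1 on schedule. The Cycle 1 durvalumab delay is any excess over 7 days after the first ceralasertib dose. Measured from Cycle 0 Day 1, an on-schedule infusion falls 28 + 7 = 35 days later, so the subject would be charged 35 − 7 = 28 days of delay.

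**The case against.** The strongest defence is that the exclusion is explicit and prespecified. The formulas match those of the main-study SAP, where there is no Cycle 0, and the opening sentence lets them work unchanged on the combination period. It governs everything below it, so each first-dose date can be read as the first dose from Cycle 1. That much stands: the sentence does a real job for durvalumab, and deleting it is not the remedy.

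Three stronger readings are tempting and are not supported.

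- *RDI is wrong as written, for example 67% in a compliant subject.* That figure arises only if the exclusion is applied to the delivered dose and ignored for the intended dose. Either consistent reading gives 100%, and the opposite mismatch gives more than 100%. What remains is an ambiguity and a blind spot, with no documented bias.
- *No output shows whether Cycle 0 drug was taken.* Total drug received is listed for all subjects and exposure swimmer plots are planned (4.3.14.1.2). Missed doses appear in the dosing listing, disposition counts subjects who received ceralasertib (4.2.1.2), and dosing deviations are summarised and listed as important protocol deviations (4.2.2). The exclusion does not say that these drop Cycle 0.
- *Adverse event rates are divided by the shortened exposure.* Percentages are per subject (4.3.14.2.2). Incidence rates are mentioned, but no person-time denominator is defined. Derived exposure does not enter the CD8 model either.

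The defence does not explain why no derived summary covers ceralasertib over the period in which safety is counted.

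**Conclusion.** The point holds for the derived ceralasertib summaries. Followed as written, the SAP omits 7 dosing days, 3,360 mg and 28 days of duration for each subject who completes Cycle 0. A subject who stops during Cycle 0 loses less than a full course, but has no derived exposure while remaining in the Safety set and able to contribute adverse events.

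The relative size depends on how long subjects stay on treatment, which the SAP does not give. Under full compliance the omitted share of duration is 50% with one combination cycle, 25% with three, 14% with six and 8% with twelve. It matters most if many subjects stop early.

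A reader might infer that every subject loses a full course, that RDI is systematically too low, or that the durvalumab dose is affected. None of these follows: the first is exact only for those who complete Cycle 0, the second depends on mixing two start dates, and durvalumab is not given in Cycle 0. No efficacy estimate or adverse event percentage changes. This is a correction to safety reporting that should be made, and it leaves the sub-study's main results untouched.

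**What to change.** Replace the opening sentence of 4.3.14.1.1; do not simply delete it.

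1. Report ceralasertib duration, cumulative dose, delays and interruptions, and RDI in three rows: Cycle 0 (ceralasertib alone), Cycle 1 onwards (combination), and total from the first Cycle 0 dose.
2. Count a late Cycle 1 start relative to Cycle 0 Day 1 as a ceralasertib delay in the total row.
3. Keep durvalumab duration, and the Cycle 1 durvalumab delay, anchored in Cycle 1.
4. Name the start date in each formula for duration, delay, intended dose and actual dose, and use the same start in the numerator and denominator of every RDI.

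The cost is SAP wording, redefined start dates in the programs and extra table rows. The dosing data are already collected.

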#### **Duration of exposure**

- Duration of exposure to ceralasertib = min(date of last dose where dose > 0 mg +o21, date of death, date of DCO) - first dose\* date +o1
- Duration of exposure to durvalumab = min(date of last dose where dose > 0 mg  $+\circ 20$ , date of death, date of DCO) first dose\* date  $+\circ 1$

\*First dose refers to earliest dose of either treatment

#### Actual duration of exposure (weeks)

- Actual exposure to ceralasertib [months] = total exposure to ceralasertib total duration of dose interruptions and dose delays
- Actual exposure to durvalumab [months] = total exposure to durvalumab total duration of dose delays

The total duration of dose delays is defined as any length of time in addition to the planned cycle length where the patient has not taken/received any of the planned doses.

- Definition of dose delay for ceralasertib: if the number of days between Day 1 of a cycle and Day 1 of the previous cycle is > 28 days, then the number of additional days above 28 days is the duration of delay.
- Definition of dose delay for durvalumab: for Cycle 1, if the number of days between the first administration of durvalumab on Day 8 and the first administration of ceralasertib on Day 1 is > 7 days, then the number of additional days above 7 days is the duration of the delay. For all subsequent cycles, if the number of days between Dayo8 of a cycle and Day 8 of the previous cycle is > 28 days, then the number of additional days above 28 days is the duration of delay.

The total duration of dose interruption is defined as any length of time during the cycle where the patient has not taken/received any of the planned doses.

• Definition of dose interruptions for ceralasertib: the total number of full-day treatment interruptions, including missed and forgotten doses. Half-day interruptions are not considered in the actual treatment exposure derivation

Note: In case the last days of cycle doses of ceralasertib are not taken (eg, Day 7) and no further medication will be taken, this is an interruption but will not be included in the total duration of dose interruptions as the total treatment exposure already includes this reduction via "date of last dose where dose > 0 mg".

The calculation of actual exposure makes no adjustment for any dose reductions that may have occurred.

Missed and forgotten doses should be recorded as a dose interruption with the reason recorded as "Patient forgot to take dose". These missed or forgotten doses are not included as dose interruptions in the summary tables, but the information appears in the listing for dosing. However, these missed and forgotten doses are considered in the derivation of actual exposure.

Dose intensity of study treatment(s) is addressed by considering relative dose intensity (RDI), where RDI is the percentage of the actual dose delivered relative to the intended dose through to treatment discontinuation. More specifically, RDI is defined as follows:

 RDI = 100% × d/D, where d is the actual cumulative dose delivered up to min(date of treatment discontinuation, date of death, data of DCO) and D is the intended cumulative dose up to the day of treatment discontinuation. D is the total dose that would be delivered if there were no modification to dose or schedule.

Intended cumulative dose is calculated by summing the individual doses that should have been received up to and including the last day of study participation according to the planned dose and schedule.

This is given by the intended dose multiplied with the number of administrations that were planned to occur. These are different per treatment component.

- Intended cumulative dose of ceralasertib [mg] = daily dose × number of dosing days =•daily dose × [7 dosing days per number of complete cycles + dosing days of incomplete cycle]:
  - If mod28(min(date of treatment discontinuation, date of DCO) date of first dose of ceralasertib + 1)  $\leq$  7 then:
    - Intended cumulative dose of ceralasertib =•240•mg × 2 × [7 × floor((min(date of treatment discontinuation, date of DCO) – date of first dose of ceralaserib +•1)/28) + mod28(min(date of treatment discontinuation, date of DCO) – date of first dose of ceralasertib + 1)]
  - Else if mod28(min(date of treatment discontinuation, date of DCO) date of first dose of ceralasertib + 1) > 7 then:

- Intended cumulative dose of ceralasertib = 240
  mg × 2 × [7 × floor(min(date of treatment discontinuation, date of DCO) date of first dose of ceralasertib +o1)/28) + 7]
- Intended cumulative dose of durvalumab [mg] = dose × number of complete cycles =01500°mg × ceil(min(date of treatment discontinuation, date of DCO) – date of first dose of durvalumab + 1)/28)

Note: ceil() refers to rounding up and floor() refers to rounding down to the next integer.  $mod_{28}(n)$  is the number n modulo 28.

Actual cumulative dose is calculated by summing all administered doses:

- ceralasertib dose = Actual dose recorded x actual frequency x duration
- durvalumab dose = Actual dose recorded

